- Significantly higher proportions of participants in the SOC arm (60% vs. 25% in the intervention arm) will progress from microalbuminuria to macroalbuminuria (uACR>300 mg/g).
- Albuminuria will fall by an average of 40% in the intervention arm and increase by an average of 10% in the SOC arm.

Study population: All HIV-positive ART-experienced (6+ months) screened individuals (n = 2,600) found to have i) confirmed microalbuminuria (mean uACR between 30-300 mg/d obtained at 2 separate measurements at least 4 and no more than 8 weeks apart), (NOTE: based on variability of individual uACR measurements, we also plan to call back Aim 1 participants having normoalbuminuria (especially those with an average uACR value in the 20-29 mg/g range) as well as Aim 1 participants having macroalbuminuria), and ii) fairly well-preserved renal function, namely an eGFR > 60 ml/min/1.73m²; will be approached for enrollment into this study. Based on recent studies at AKTH among HIV positive adults, we anticipate that a minimum of 18% of screened patients (n~460) will be eligible. Therefore, with a target sample size equal to

280 (see Section 10.0), 59% of eligible patients would need to consent for this Aim 2 study.

Primary Endpoints:

- i) Regression from microalbuminuria (uACR=30-300 mg/g) to normoalbuminuria (uACR < 30 mg/g)
- ii) Progression from microalbuminuria (uACR=30-300 mg/g) to macroalbuminuria (uACR > 300 mg/g) by study arm
- iii) Mean change in uACR

Secondary Endpoints:

i) Doubling of serum creatinine from baseline; ii) All-cause mortality (**NOTE**: Planned follow-up is two years for all participants), iii) Proportion experiencing a 40% decline in eGFR (using CKD-EPI-Cr-CyC equation), iv) Mean change in eGFR over time (using CKD-EPI-Cr-CyC equation), and v) change in clinical/performance status (as ascertained via two measures, specifically the WHO quality of life (WHOQOL-HIV) tool (31 questions)^{107,108} and the Karnofsky performance score)¹⁰⁹.

1.3 Specific Aim 3

Specific Aim 3: To determine whether the *APOL1* HR genotype is associated with worse longitudinal kidney outcomes among HIV-positive Nigerians with prevalent albuminuria, with regard to progression of albuminuria and eGFR decline.

Hypothesis: After two years of follow-up, independent of baseline uACR, eGFR, and/or treatment assignment:

- Study participants with the HR genotype will have a more rapid kidney function decline (median eGFR change) compared to those with the LR genotype.

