Longitudinal Study Assessments: All enrolled patients will undergo the following tests at baseline and then every 3 months while on study, until completing 2 years of followup: serum cystatin C, blood pressure, serum electrolytes (creatinine, potassium, sodium, chloride, bicarbonate, and urea), and uACR. Clinical performance status (as measured via the WHOQOL-HIV tool and the Karnofsky performance score) will be evaluated at baseline and at 12 and 24 months. If participant is a female with reproductive potential, she will undergo urine pregnancy testing every 3 months (please see below in **NOTE**). All enrolled aim 2 study participants will have their APOL1 genotype data (i.e. whether HR or LR genotype) available prior to completing study follow-up (see Study Timeline). All patients will undergo routine standard laboratory monitoring as per existing guidelines; specifically, CD4+ cell count and viral load testing (q 6 monthly), liver function test monitoring (at month 1, 3, and 6, and then q 6 monthly following ART initiation), etc., as per Nigeria standard of care (SOC). All enrolled patients will undergo a blood pressure check and have serum electrolytes tested at week 1 and month 1 following study initiation and any changes in dose as part of a brief safety check. All enrolled patients will undergo hepatitis B and C screening at baseline. Additional funds have been allocated for patients to undergo unscheduled safety monitoring (up to two additional times per year) as needed, while on study.

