Statistical analysis plan: Our first approach will be to perform an intent-to-treat analysis, but we will also perform an on-treatment analysis to compare these data and present all available findings. *Primary analysis*: We will test the hypotheses that regression and progression rates are different across arms using multivariable Cox regression models with the intervention variable (randomization to RAAS [yes/no]) as the primary predictor variable, adjusting for baseline (pre-randomization) covariates including baseline uACR, *APOL1* renal risk variants, CD4+ cell count, blood pressure

ART regimen (DTG vs. other), and the presence/absence of comorbid medical conditions (hypertension, cardiovascular disease). To relax linearity assumptions, baseline uACR will be included in models using restricted cubic splines.¹³⁸ Primary analyses will be intention to treat, although we also plan to perform "per protocol" analysis. We will also test the impact of study arm on uACR using a linear mixed effects model to account for within patient correlation with the outcome of 3-monthly uACR values (with primary endpoints obtained by evaluating the uACR and other key renal outcomes at 18 and 30 months given that all enrolled study participants will not be placed or sustained on their maximum tolerated lisinopril dose or matched placebo until 6 months after study enrollment). The model will also adjust for the baseline covariates given above. For this analysis, we anticipate log-transforming uACR to meet modelling assumptions, although other transformations will be considered if needed.

Secondary analyses: Analyses for secondary endpoints will be similar to that described above. Time-to-event outcomes (doubling of serum creatinine from baseline, all-cause mortality, 40% decline in eGFR, and tenofovir toxicity) will be assessed using multivariable Cox regression models. Continuous outcomes (eGFR, quality of life metrics, and blood pressure) will be analyzed using mixed effects models after proper transformation of the outcome variable, if necessary. Baseline covariates listed above will be included in all secondary analyses.

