Statistical analysis and considerations: Analyses for Aim 3 will be the same as those outlined in Aim 2, except the predictor of interest will be APOL1 haplotype (high risk vs. low risk) instead of intervention arm; analyses will adjust for intervention arm (similar to how analyses of Aim 1 adjusted for APOL1 genotype). Assuming that ~30% (n = 84) of Aim 2 study participants have the high risk genotype, namely 2 copies of the risk variants (G1/G1, G1/G2, or G2/G2), with the remainder of Aim 2 study participants (n =196) having the low risk genotype (carrying no or one risk allele [G0/G0, G0/G1, and G0/G2]), and that the rate of progression will be similar to that hypothesized in Aim 2, we anticipate having 80% power to detect hazard ratios on the order of 2.4 to 3.2. Specifically, if the rate of regression is 22% (e.g., 10% and 25% in the SOC and intervention arms, respectively), we will have 80% power to detect a hazard ratio of 3.2 between the low and high risk genotypes; if the rate of regression is 35% (e.g., 20% and 40% in the SOC and intervention arms, respectively), we will have 80% power to detect a hazard ratio of 2.4. With regards to progression, if the overall event rate is 42.5%, we anticipate having 80% power to detect a hazard ratio of 2.1 between the high and low risk genotypes; if the overall rate of progression is 28%, we anticipate approximately 80% power to detect a hazard ratio of 2.5. Analyses will be repeated treating number of risk alleles (0, 1, or 2) as a categorical variable to investigate differences in risks when having 0 vs. 1 risk allele.

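### The covariate list for the secondary and Aim 3 models does not name baseline eGFR or the baseline WHOQOL-HIV and Karnofsky scores: a modest efficiency loss in Aim 2, and in Aim 3 a mismatch with the stated hypothesis

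*Combined protocol and SAP*

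**What the plan says.** In Section 8.0, Specific Aim 2, the primary Cox models are specified as "adjusting for baseline (pre-randomization) covariates including baseline uACR, *APOL1* renal risk variants, CD4+ cell count, blood pressure", continuing with "ART regimen (DTG vs. other), and the presence/absence of comorbid medical conditions (hypertension, cardiovascular disease". The primary uACR analysis is a "linear mixed effects model to account for within patient correlation with the outcome of 3-monthly uACR values", with the same covariates, so uACR is adjusted for its own baseline.

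The secondary analyses are to be similar. For the continuous endpoints, "Continuous outcomes (eGFR, quality of life metrics, and blood pressure) will be analyzed using mixed effects models". The covariate instruction is "Baseline covariates listed above will be included in all secondary analyses".

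For Aim 3, Section 8.0 says "Analyses for Aim 3 will be the same as those outlined in Aim 2, except the predictor of interest will be APOL1 haplotype"; the one further adjustment named is study arm. Section 1.3 introduces the Aim 3 hypothesis with "After two years of follow-up, independent of baseline uACR, eGFR, and/or treatment assignment", and its eGFR part concerns faster decline, expressed as median eGFR change.

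The baseline data exist. Section 5.0 (Longitudinal Study Assessments) says "All enrolled patients will undergo the following tests at baseline and then every 3 months while on study", and the tests include creatinine and cystatin C, from which eGFR is computed. The same paragraph schedules WHOQOL-HIV and Karnofsky at baseline, 12 and 24 months.

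**The concern.** uACR and blood pressure are both outcomes, and both appear in the list at their baseline value. eGFR, WHOQOL-HIV and Karnofsky are outcomes whose baseline value is not named. Randomisation is stratified on uACR and APOL1 alleles (Section 5.0), not on eGFR, so the design does not supply the missing term.

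Two things are at stake. In Aim 2, the arm comparison for continuous eGFR and quality of life gives up precision that the collected data could provide. In Aim 3, genotype is not randomised, and Section 1.1 expects high-risk carriers to have lower baseline eGFR. Of the three factors the hypothesis claims independence from, uACR and arm are adjusted for and eGFR is not. The plan also does not say how the baseline eGFR value enters the mixed model, so a choice that can move the result is left open until data are in hand.

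**Working it through.** **Inputs.** 126 per arm after loss to follow-up; Table S5 detectable difference for mean change in eGFR of 0.35 SD (80% power) and 0.41 SD (90% power), in Appendix B. Table S5 states no alpha; 5% two-sided is taken from Table S8, which shows the same 0.35 and 0.41. Aim 3 groups are 84 high-risk and 196 low-risk (Section 8.0). The baseline-to-follow-up correlation r is not in the documents and is assumed throughout.

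**Step 1: reproduce Table S5.** Detectable difference = (z for alpha + z for power) × √(2/126).
- 80%: (1.960 + 0.842) × 0.126 = 0.353 SD.
- 90%: (1.960 + 1.282) × 0.126 = 0.408 SD.

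In reverse, 0.35 SD gives 79.3% power and 0.41 SD gives 90.2%. Table S5 is confirmed.

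**Step 2: Aim 2 gain on the change scale.** With equal variance σ² at both times, a change score has variance 2(1 − r)σ² and a baseline-adjusted analysis has (1 − r²)σ². The ratio is (1 + r)/2, so the detectable difference becomes 0.353 × √((1 + r)/2).

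| r (assumed) | variance ratio | variance reduction | detectable difference (SD of change) | power at 0.35 SD |
|---|---|---|---|---|
| 0.6 | 0.80 | 20% | 0.316 | 87% |
| 0.7 | 0.85 | 15% | 0.325 | 85% |
| 0.8 | 0.90 | 10% | 0.335 | 83% |

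The gain shrinks as r rises, because a change score then already removes most between-person variation.

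**Step 3: Aim 3.** Suppose carriers start d = 0.3 SD lower in eGFR (assumed) and genotype has no association with follow-up eGFR given baseline. Without baseline eGFR in the model, the expected high-risk minus low-risk difference is −r·d for follow-up level and +(1 − r)·d for change. The standard error for level is √(1/84 + 1/196) = 0.130 SD; for change it is 0.130 × √(2(1 − r)). A wider range of r is shown.

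| r (assumed) | level: difference (SD) | level: rejection at nominal 5% | change: difference (SD) | change: rejection at nominal 5% |
|---|---|---|---|---|
| 0.5 | −0.15 | 21% | +0.15 | 21% |
| 0.7 | −0.21 | 36% | +0.09 | 14% |
| 0.9 | −0.27 | 54% | +0.03 | 8% |

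With d = 0.1 SD, the rejection rates are 5% to 11%. The sign depends on whether level or change is modelled, and the size depends on d and r. The documents give neither d nor r.

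**The case against.** The strongest reply has five parts.

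- **The list is not closed.** It is introduced by the word including, and the secondary analyses are to resemble a template that adjusts uACR for its own baseline. Baseline eGFR might also enter the mixed model as an outcome row; with a common baseline mean, that recovers most of the Aim 2 precision. This stands as a limit on the wording: the baselines are not named, which is different from being discarded. It does not close the gap, because the secondary sentence points only to covariates already listed and no outcome-row model is described.
- **Aim 2 is randomised.** This stands. The arm comparison is unbiased either way.
- **The gain could be read as much larger.** A reader might apply 1 − r² to Table S5 and infer a variance reduction of 36%, 51% or 64% for r of 0.6, 0.7 or 0.8. That treats 0.35 SD as the SD of a follow-up level analysed without baseline. Table S5 and the endpoint are both labelled mean change, so the documents do not support that reading.
- **Confounding is the wrong word for Aim 3.** A reader might infer that an entry difference in eGFR would be reported as faster decline in carriers. If carriers start lower and both groups decline in parallel, a change analysis shows no difference. Genotype also precedes baseline eGFR, which is a possible consequence of it and not a classical confounder. Adjustment changes the question: under parallel decline with d = 0.3 SD, the baseline-adjusted difference is −(1 − r)·d, or −0.15, −0.09 or −0.03 SD for r of 0.5, 0.7 or 0.9. All of this stands, and it is why the Aim 3 result needs to be described as an association given baseline eGFR.
- **The event endpoints differ.** A 40% eGFR decline and a doubling of creatinine are already defined relative to each participant's own baseline, so the precision argument applies mainly to the continuous outcomes. For tenofovir toxicity, 2% of 252 is about 5 events; a further covariate there is not warranted.

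The eGFR entry floor of 60 mL/min/1.73m² may also narrow any genotype difference at baseline.

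**Conclusion.** The omission is confirmed in the text, and nothing elsewhere in the plan supplies the term for the Aim 2 or Aim 3 models.

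For Aim 2 it is a modest loss of efficiency on secondary endpoints and no source of bias. The 10% to 20% variance figure rests on three assumptions: that Table S5 is in SDs of change, that variance is equal over time, and that r lies between 0.6 and 0.8. The gain is larger only if follow-up levels are analysed without baseline.

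For Aim 3 the models as written do not test the hypothesis as stated, because two of the three named factors are adjusted for and baseline eGFR is not. A reader might infer that Aim 3 is therefore unable to address its question at all. That goes too far: the hypothesis says and/or, the data are there, and one added term aligns model and hypothesis. The rejection rates in the working illustrate sensitivity to an unspecified choice; they are not forecasts.

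**What to change.** In Section 8.0, Specific Aim 2, secondary analyses, add that the mixed model for each continuous secondary outcome (eGFR, WHOQOL-HIV, Karnofsky) includes the baseline value of that outcome as a covariate, and that the baseline visit is then not also used as an outcome row. Leave the tenofovir-toxicity model without the extra term.

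In Section 8.0, Specific Aim 3, add that the models testing the Section 1.3 hypothesis include baseline eGFR alongside baseline uACR and study arm, and that the result is reported as an association given baseline eGFR.

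The cost is a few sentences in the analysis plan. The values are already collected, so no visit, assay or sample-size change follows.

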Nigeria standard of care: The Nigeria HIV/AIDS adult treatment guidelines recommend a baseline assessment of all HIV-positive patients to include a complete history and physical examination, staging of disease with clinical and immunological classification of the patient, and review of laboratory results. In addition, an evaluation of nutritional and psychosocial status, assessment of readiness for therapy, and development of patientspecific adherence strategy is recommended for all patients. All HIV-positive patients, regardless of CD4+ cell count (commonly referred to as the "Test-and-Start" or "Treat All" strategy) are started on ART. First line regimens include: tenofovir (TDF) + lamivudine (3TC) + efavirenz (EFV); TDF + 3TC + nevirapine (NVP); zidovudine (AZT) +3TC (or emtricitabine [FTC]) + EFV and AZT +3TC (or FTC) + NVP. A boosted protease inhibitor plus 2 nucleoside reverse transcriptase inhibitors (NRTIs) are recommended for second-line ART, and available protease inhibitors include ritonavirboosted lopinavir and atazanavir. The government of Nigeria will be transitioning to TLD (tenofovir, lamivudine, plus the integrase strand inhibitor dolutegravir) during 2018-2019. As a result, all HIV positive persons (> 10 years of age and weighing > 30 kilograms) will be switched to TLD during this transition period in accordance with national guidelines/WHO recommendations. In patients with renal insufficiency, i.e. a documented increase in serum creatinine, the guidelines recommend ART regimen dosage modifications if the calculated creatinine clearance (CrCl) is reduced at baseline (i.e. not initiating tenofovir in adult patients having a calculated eGFR of < 50 ml/min/1.73m² or if at any time during follow-up their CrCl decreases significantly (i.e. confirmed to $< 50 \text{ ml/min/1.73m}^2$ from their baseline values). Modifications include switching patients from tenofovir to abacavir as well as investigating potential causes of their worsening renal function (i.e. looking for pre-renal causes such as dehydration, post-renal causes (prostatic obstruction, nephrolithiasis, and/or intra-renal causes such as initiation of new potentially nephrotoxic medications (such as traditional medicines, etc.). Of note, patients switched to dolutegravir (from efavirenz or nevirapine) as part of the soon to commence TLD rollout may also experience a sustained increase in their serum creatinine coupled with a corresponding decrease in their calculated eGFR. In brief, for a period of up to 48 weeks following dolutegravir (DTG) initiation, it is anticipated that study participants may experience a modest (0.2 mg/dL) increase in serum creatinine¹²⁷⁻¹²⁹ that will not lead to significant changes in uACR values but will be lead to aim 2 study participants having a "new baseline eGFR" that is unrelated to study medication and based on the literature using iohexol ¹³⁰ will not represent a true change in eGFR; but nonetheless will still need to be accounted for in the analysis plan. NOTE: Given the known limitations of CysC-based equations for HIV-positive individuals, from an analysis standpoint, the team will utilize/rely on significant changes in serum creatinine (sCr) safety monitoring/reporting among DTG-treated study participants. Patients with reductions in CrCl should undergo an evaluation for potential causes of decreased renal function and have serum creatinine monitored more frequently until

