 - 3-day safety phone call (post initiation of study medication (or matched placebo) evaluating for possible adverse events (and if during phone safety check screening there is any suggestion of a possible adverse event, then the participant will be instructed to come in to clinic for immediate evaluation including blood draw and blood pressure check)
 - 7-day safety clinic visit (blood draw plus blood pressure check)
 - 1-month safety clinic visit (blood draw plus blood pressure check)
 - Unscheduled study visit (study participants to contact study personnel at any time and if have signs/symptoms at suggestive of an adverse event, they will come to clinic for immediate assessment)
- c) Dose escalation of study medication (increase from 10 mg/d of lisinopril or matched placebo to 20 mg/d) (scheduled to take place at the 3- month study visit);
 - 3-day safety phone call (post initiation of study medication (or matched placebo) evaluating for possible adverse events (and if during phone safety check screening there is any suggestion of a possible adverse event, then the participant will be instructed to come in to clinic for immediate evaluation including blood draw and blood pressure check)
 - 7-day safety clinic visit (blood draw plus blood pressure check)
 - 1-month safety clinic visit (blood draw plus blood pressure check)
 - Unscheduled study visit (study participants to contact study personnel at any time and if have signs/symptoms at suggestive of an adverse event, they will come to clinic for immediate assessment)

- d) Dose escalation of study medication (increase from 20 mg/d of lisinopril or matched placebo to 40 mg/d) (scheduled to take place at the 5- month study visit);
 - 3-day safety phone call (post initiation of study medication (or matched placebo) evaluating for possible adverse events (and if during phone safety check screening there is any suggestion of a possible adverse event, then the participant will be instructed to come in to clinic for immediate evaluation including blood draw and blood pressure check)
 - 7-day safety clinic visit (blood draw plus blood pressure check)
 - 1-month safety clinic visit (blood draw plus blood pressure check)
 - Unscheduled study visit (study participants to contact study personnel at any time and if have signs/symptoms at suggestive of an adverse event, they will come to clinic for immediate assessment

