In conversations with the DSMB, concerns were brought up regarding the nationwide switch to dolutegravir (DTG) and its potential impact on results. As sensitivity analyses, we will repeat the primary and secondary analyses listed above but also include any switch to a DTG-containing regimen post-randomization as a time-varying covariate. Our rationale for not including DTG-switch in the primary analysis, is that post-randomization variables (such as a switch to DTG) could be affected by treatment assignment and adjusting for it could therefore potentially bias results. However, we believe that the transition to DTG will not be affected by treatment assignment, in which case these analyses will be fine. If post-randomization DTG-uptake does differ by treatment arm (>5%), then we will investigate whether DTG-use is a mediator between treatment assignment and any of the primary or secondary outcomes listed above. Mediation analyses will follow the approaches outlined in VanderWeele TJ (2015) Explanation in Causal Inference. Finally, we will investigate whether the effect of assignment to ACEi could be modified by DTG-use. To do this, we will repeat the primary and secondary analyses but include an interaction between time-varying DTG-use and treatment assignment.

Potential difficulty reaching desired sample size: Our microalbuminuria prevalence estimates among HIV positive adults engaged in care at AKTH are conservative, as they are based on published data from this same hospital among asymptomatic HIV positive adults, and we anticipate that only approximately 59% of those eligible for our aim 2 study will need to consent/enroll in order for us to reach our target sample sizes. Therefore, with a target sample size equal to 280, 59% of eligible patients would need to consent for Study Aim 2.

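### The test of whether DTG modifies the lisinopril effect has no arm-by-time term, so part of any build-up during titration is credited to DTG

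*Combined protocol and SAP*

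**What the plan says.** Three parts of the plan meet here.

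- **The test.** The DTG paragraph of the Aim 2 statistical analysis plan (Section 8.0) asks whether DTG use could modify the effect of assignment to ACEi: "we will repeat the primary and secondary analyses but include an interaction between time-varying DTG-use and treatment assignment". It gives no significance level or decision rule.
- **The models repeated.** Regression and progression are analysed "using multivariable Cox regression models with the intervention variable (randomization to RAAS [yes/no]) as the primary predictor variable", and uACR "using a linear mixed effects model to account for within patient correlation with the outcome of 3-monthly uACR values". Baseline covariates are listed, including DTG versus other ART. An arm-by-time term is not listed for either model.
- **Timing.** The same section notes that participants "will not be placed or sustained on their maximum tolerated lisinopril dose or matched placebo until 6 months after study enrollment". Section 6.0 has the last dose step "scheduled to take place at the 5- month study visit". Visits are "every 3 months while on study, until completing 2 years of followup" (Section 5.0). On the national programme, Section 5.0 says HIV-positive people over the stated age and weight limits "will be switched to TLD during this transition period in accordance with national guidelines/WHO recommendations".

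The only condition the plan attaches to its DTG analyses is that switching should not depend on arm. It states this for the sensitivity analysis with DTG as a time-varying covariate, and adds no further condition for the interaction.

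**The concern.** A participant who switches contributes off-DTG time early in follow-up and on-DTG time later. The early part is also when the study drug is below its maximum tolerated dose. The DTG-by-arm coefficient therefore mixes two contrasts: on versus off DTG, and later versus earlier treatment effect. A Cox baseline hazard, or a visit main effect in the mixed model, absorbs a time trend common to both arms. Neither absorbs a trend in the difference between arms. Balance of switching between arms does not help, because the confounding is with time since randomisation and not with arm.

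The DTG analyses were added after the DSMB raised the national switch. If lisinopril works and takes some months to do so, this test leans towards finding that it works better on DTG. A true interaction in the other direction could be masked.

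**Working it through.** **1. The plan's own figures.** Schoenfeld power is Φ(|ln HR|·√(d/4) − z), with z = 2.387 for two-sided 0.017.
- Regression, 53 events, HR 2.5: 0.916 × 3.640 − 2.387 = 0.948, so power is 0.829 (plan 0.828).
- Progression, 107 events, HR 0.42: 0.868 × 5.172 − 2.387 = 2.10, so power is 0.982 (plan 0.984).

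The plan's inputs reproduce. It gives no error rate for the DTG interaction, so that has to be simulated.

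**2. Direction by hand (uACR).** The hypothesised effect (40% fall versus 10% rise, Section 1.2) is ln(0.60/1.10) = −0.606. Assume half of it at month 3 and all of it from month 6, with 90% of participants switching evenly over months 0-12.
- The share on DTG at the eight visits is 0.225, 0.45, 0.675, then 0.9 five times. The sum is 5.85 on and 2.15 off.
- Mean fraction of full effect in on-DTG visits: (0.225 × 0.5 + 5.625)/5.85 = 0.981.
- Mean fraction in off-DTG visits: (0.775 × 0.5 + 1.375)/2.15 = 0.820.
- Difference: 0.161 × (−0.606) = −0.10 log units, with no DTG effect present.

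This is the unweighted contrast. A mixed model relies more on before-and-after contrasts within a person, and gives about −0.15.

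**3. Simulation.** Set-up: 126 per arm, eight 3-monthly visits, true interaction zero, switching independent of arm, nominal 5%.
- Mixed model: SD of log uACR 0.58 (Table S1), within-person correlation 0.5, visit as a factor, build-up as in step 2.
- Cox models: 3-month intervals, no effect in months 0-3, half in 3-6, full after. Progression uses HR 0.42 with 60% in the SOC arm; regression uses HR 2.5 with 16%.

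Cells show the spurious interaction and the rejection rate. The figure after the arrow is the rate once an arm-by-time term is added (arm x visit in the mixed model, arm x first 6 months in Cox).

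| DTG uptake (assumed) | uACR mixed model | Cox progression | Cox regression |
|---|---|---|---|
| 90% switch, months 0-6 | −0.25, 89.2% → 4.8% | −0.50, 23.5% → 4.2% | +0.39, 6.2% → 3.8% |
| 90% switch, months 0-12 | −0.15, 85.0% → 6.0% | −0.47, 21.5% → 5.0% | +0.26, 7.8% → 4.5% |
| 90% switch, months 0-24 | −0.10, 53.5% → 6.8% | −0.30, 11.0% → 2.8% | +0.23, 3.5% → 3.8% |
| 50% at baseline, 40% switch 0-12 | −0.14, 46.0% → 6.0% | −0.22, 6.5% → 2.5% | +0.20, 4.0% → 2.8% |
| 85% at baseline, 10% switch 0-12 | −0.10, 12.8% → 3.5% | −0.11, 5.5% → 3.8% | −0.03, 1.5% → 1.0% |

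Monte Carlo error is about 1 point near 5% and up to 2.5 points in mid-range.

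**4. Sensitivity.**
- Further runs under other switching assumptions gave 25-92% (mixed model), 7-27% (progression) and 1-6% (regression).
- A 0.15/0.5/1 ramp at the plan's hazard ratios gave 19%, 13%, 5% and 4% for progression with 0%, 40%, 80% and 80% on DTG at baseline. In the last case the remaining switches were spread over 24 months. Regression gave 10%, 6%, 1% and 3%.
- Within-person correlation 0.3 or 0.7, in the second row of the table: 67% and 97% (mixed model).
- A smaller uACR effect of 0.24 with the same build-up: 12-21%.
- Effect complete by month 3: 3.5-7% (mixed model) and at most about 7% (Cox).
- After correction, the mixed-model interaction is within 0.01 of zero wherever the effect builds up. The single Cox term leaves up to about 0.16 in absolute log-HR in the sparsest cells.

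**The case against.** The strongest reply is that the plan is silent on arm x visit and does not exclude it. It says uACR and other renal outcomes are evaluated at 18 and 30 months because of the titration period, and separate contrasts at two times imply an arm effect that varies by visit. That stands as a pointer for the mixed model. But no such term is written, the Cox models have a single arm effect, and month 30 lies beyond the two-year follow-up, so the sentence cannot be applied as it stands.

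Second, many participants may already have been on DTG at randomisation. The transition was placed in 2018-2019, and Section 3.0 reports about 380 of the planned 2,600 Aim 1 participants when data were reviewed in January 2019. This also stands: the inflation shrinks as the baseline share rises. The documents do not give that share.

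Third, this is a supplementary analysis without a decision rule. That limits the consequence but does not remove the bias.

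A reader might infer more than the documents support:
- **That the test simply compares early with late follow-up.** Baseline DTG users, never-switchers and varied switch times all contribute, and only part of the build-up is misattributed.
- **That the Cox tests fail badly.** High rates there need an effect that grows over the whole 24 months, or hazard ratios stronger than the stated 0.42 and 2.5. The documents describe only a 5-6 month titration.
- **That the main result is in doubt.** The primary models do not contain the DTG interaction.

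**Conclusion.** The concern holds in a limited form. As written, the DTG interaction is confounded with time since randomisation, and independence of switching from arm does not cure this. With half effect at month 3 and full effect from month 6:

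- **uACR mixed model:** the problem is large, with about 25-90% false rejection, falling to 13% when 85% start on DTG and only 10% switch.
- **Cox progression:** modest, about 5-27%. The largest spurious ratio of hazard ratios is exp(−0.50) = 0.61.
- **Cox regression:** rejection is near nominal at 1-10% because events are few. The estimate is still biased, by up to exp(0.39) = 1.48.

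These sizes rest on switch timing, baseline DTG share and speed of onset, none of which the documents give. If the effect is complete by the first 3-month visit, there is no distortion. The term should be specified before analysis.

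**What to change.** In the DTG paragraph of the Aim 2 statistical analysis plan:

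1. Add arm x visit to every mixed model that carries DTG-use x arm.
2. In the progression and regression Cox models, add one arm x first-6-months term, or restrict the interaction to follow-up after month 6.
3. Report arm x baseline DTG regimen alongside. That variable is already a covariate and precedes randomisation.
4. For mortality, doubling of creatinine and tenofovir toxicity, do not fit arm-by-time terms. Report the DTG interaction descriptively, with the caveat that it is confounded with time since randomisation.
5. Report when DTG was started relative to randomisation.

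A richer Cox correction (arm by three phases plus arm by linear time) should not be used. For regression, with 0-40% on DTG at baseline, it gave about 20% unstable fits, against 0-6% without it. At an 8% SOC event rate it failed in 72-80% of runs, and at 2% in 96%.

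The cost is a few sentences and no new data. The interval for the DTG interaction widens: the standard error for progression is about 35-50% larger if nobody is on DTG at baseline, and less otherwise. The primary analysis does not change.
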